## SCHEMA

## 1.0 Introduction and Background

Increased levels of epinephrine induced by stress inhibit apoptosis and accelerate tumor progression in mouse models of prostate cancer via  $\beta$ 2-adrenergic receptor (ADRB2)/ cAMP-dependent protein kinase (PKA)/ BCL2-associated death promoter (BAD) signaling pathway . Furthermore, analysis of 20 prostate biopsies showed significant positive correlation between increased blood epinephrine levels and activation of the ADRB2/PKA/BAD signaling pathway in the prostate gland of men . Because PKA can phosphorylate several substrates in addition to BAD, it is beneficial to analyze phosphorylation of both S75 BAD and S133 CREB to increase assay specificity. Further, antibodies to pS133CREB may be more sensitive compared to pS75 BAD-specific antibodies.

To further improve the specificity and sensitivity of measuring activation of ADRB2 signaling pathway, we have compared mRNA profiles in prostate cancer C42 cells exposed to vehicle or epinephrine using Affimetrix arrays. This comparison identified several transcripts induced by activation of ADRB2 pathway. Should the specificity of these induced transcripts be confirmed, the analysis of these transcripts in collected prostate tissues will also be conducted.

Recently, in a breast cancer mouse model, it has been shown that chronic stress promotes metastasis and that treatment with a beta-blocker can prevent metastasis . Similarly, an association between dysregulation of stress-related signaling pathways, especially the adrenergic pathway and lethal prostate cancer has been reported . These data suggest that stress and ADRB2/PKA/BAD signaling may play an important role in prostate cancer pathophysiology.

In patients with advanced prostate cancer who experience increased stress, elevated epinephrine levels may contribute to inhibition of apoptosis and, hence, therapeutic resistance. Conversely, inhibiting the ADRB2/PKA/BAD signaling pathway by ADRB2-selective beta blockers could be a therapeutic option for patients with increased epinephrine levels . Several epidemiological studies have addressed a potential correlation between the use of beta blockers and prostate cancer incidence and mortality, but they reached contradictory conclusions . The results of the most recent studies suggest that activation of ADRB2 is likely to contribute to prostate cancer progression but does not increase prostate cancer incidence. Likewise improvement in overall survival was recently reported for ovarian cancer patients who took beta-blockers . Most patients in these studies took  $\beta$ 1-selective blockers, which are poor inhibitors of ADRB2 signaling. A recent study that focused on patients who took propranolol that inhibits ADRB2 signaling reported significant decrease in incidence of several cancers including prostate cancer . Furthermore, our data from preclinical models of prostate cancer suggest that not all patients will respond to therapy with  $\beta$ 2-selective blockers due to compensatory signaling pathways that inhibit apoptosis despite of the inactivation of ADRB2/PKA axis. Thus, patients in whom ADRB2/PKA is the major pathway that controls BAD phosphorylation and apoptosis are likely to benefit from ADRB2-selective blockers. In contrast, for patients with multiple redundant

pathways that converge on BAD, the ADRB2-selective blockers will likely need to be given in combination with inhibitors of other signaling pathways.

Beta blockers are commonly administered in the perioperative period. Perioperative beta blocker use has been associated with lower 30-day mortality rates, although the benefit is stronger for those undergoing cardiovascular surgery, and the benefit in the setting of non-cardiac surgery remains controversial . In a 1991 study of women in the perioperative period, a one-time preoperative dose of oral propranolol of 80 mg was well-tolerated and resulted in less anesthetic use . In a more recent randomized study, perioperative doses of 20mg or 40mg were used to reduce anxiety among surgery patients. With the administration of 20mg of oral propranolol, there was a significant decrease in anxiety with fewer cardiovascular effects than the 40mg dose. In the current study, the use of propranolol will be continuously monitored for safety events. Any safety concerns that arise as defined in the protocol will trigger a dose reduction for subsequent patients. Additionally, an interim analysis will assess safety.

## **2.0 Objectives**

### **2.1 Primary Objective**

- 2.1.1 To compare activation of ADRB2/PKA/BAD signaling pathway in the prostate glands of men two hours after taking or not taking propranolol prior to prostate biopsy or prostatectomy, as indicated by phosphorylated CREB.

### **2.2 Secondary Objectives**

- 2.2.1 To compare activation of ADRB2/PKA/BAD signaling pathway in the prostate glands of men two hours after taking or not taking propranolol prior to prostate biopsy or prostatectomy as indicated by phosphorylated BAD.
- 2.2.2 To determine the difference in candidate transcript levels associated with ADRB2/PKA activation between individuals two hours after taking propranolol or not taking propranolol prior to prostate biopsy or prostatectomy.
- 2.2.3 To determine plasma propranolol levels in individuals taking propranolol two hours after administration prior to prostate biopsy or prostatectomy.
- 2.2.4 To determine if plasma catecholamine levels in men with prostate cancer can be used as a biomarker to identify patients who show activation of ADRB2 signaling pathway in prostate tumors.

- 2.2.5 To determine perceived stress level differences in men with prostate cancer prior to prostate biopsy or prostatectomy to examine possible association between perceived stress level and catecholamine levels in blood and activation of ADRB2 pathway in tumors
- 2.2.6 To determine perceived distress level differences in men with prostate cancer prior to prostate biopsy or prostatectomy to examine possible association between distress level and catecholamine levels in blood and activation of ADRB2 pathway in tumors.

## **3.0 Study Population**

Patients recruited will be individuals scheduled for prostate biopsy or prostatectomy. For this study, 60 individuals will be recruited. Patients will be randomized to receive the treatment (or not) for a total of 30 patients receiving propranolol prior to biopsy or prostatectomy and 30 patients receiving no treatment. It is expected that approximately 10 (5 patients in each group) may have non-evaluable tumor tissue. In case the number of evaluable tumors will be less than 25 for each group, more patients will be recruited to accumulate 25 evaluable samples for each group.

### **3.1 Inclusion criteria:**

- 1) Men >18 years of age
- 2) Patients undergoing prostate biopsy or prostatectomy
- 3) Individuals able to understand and willing to sign an IRB-approved informed consent document

### **3.2 Exclusion criteria:**

- 1) Men taking propranolol daily for any reason are excluded
- 2) Men with baseline SBP <120 or HR <63
- 3) Men unable to swallow pills
- 4) History of current or past medical or psychiatric illness that would make participation difficult or not feasible at the discretion of the principal investigator or co-investigators.

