## **4.0 Methods**

### **4.1 Registration Procedures**

All patients entered on any WFBCCC trial, whether treatment, companion, or cancer control trial, **must** be registered, within 24 hours of Informed Consent, into WISER. Patients **must** be registered prior to the initiation of treatment.

You must perform the following steps in order to ensure prompt registration of your patient:

1. Complete the Eligibility Checklist (Appendix A)
2. Complete the Protocol Registration Form (Appendix B)
3. Alert the Cancer Center registrar by phone, *and then* send the signed Informed Consent Form, Eligibility Checklist and Protocol Registration Form to the registrar, either by fax or e-mail.

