#### Contact Information:

Protocol Registrar [contact]

Protocol Registrar [contact]

Protocol Registrar E-MAIL ([[contact]](mailto:[contact]))

\*Protocol Registration is open from 8:30 AM - 4:00 PM, Monday-Friday.

4. Fax/e-mail ALL eligibility source documents with registration. Patients **will not** be registered without all required supporting documents.

Note: If labs were performed at an outside institution, provide a printout of the results. Ensure that the most recent lab values are sent.

To complete the registration process, the Registrar will:

- assign a patient study number
- Randomized Group Assignment
- register the patient on the study

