## 13.0 Adverse Events List and Reporting Requirements

### 13.1 Adverse Event List for Propranolol

Cardiovascular: Bradycardia; congestive heart failure; intensification of AV block; hypotension; paresthesia of hands; thrombocytopenic purpura; arterial insufficiency, usually of the Raynaud type.

Central Nervous System: Light-headedness, mental depression manifested by insomnia, lassitude, weakness, fatigue; catatonia; visual disturbances; hallucinations; vivid dreams; an acute reversible syndrome characterized by disorientation for time and place, short-term memory loss, emotional lability, slightly clouded sensorium, and decreased performance on neuropsychometrics. For immediate-release formulations, fatigue, lethargy, and vivid dreams appear dose-related.

Gastrointestinal: Nausea, vomiting, epigastric distress, abdominal cramping, diarrhea, constipation, mesenteric arterial thrombosis, ischemic colitis.

Allergic: Hypersensitivity reactions, including anaphylactic/anaphylactoid reactions, pharyngitis and agranulocytosis; erythematous rash, fever combined with aching and sore throat; laryngospasm, and respiratory distress.

Respiratory: Bronchospasm.

Hematologic: Agranulocytosis, nonthrombocytopenic purpura, thrombocytopenic purpura.

Autoimmune: Systemic lupus erythematosus (SLE).

Skin and mucous membranes: Stevens-Johnson Syndrome, toxic epidermal necrolysis, dry eyes, exfoliative dermatitis, erythema multiforme, urticaria, alopecia, SLE-like reactions, and psoriasisiform rashes. Oculomucocutaneous syndrome involving the skin, serous membranes and conjunctivae reported for a beta blocker (practolol) have not been associated with propranolol.

Genitourinary: Male impotence; Peyronie's disease.

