## Appendix A – Subject Eligibility Checklist

IRB Protocol No. 00043227	WFCCC Protocol No. 8 5 7 1 6
Study Title: Evaluating the effect of the ADRB2 blockers on PKA/BAD/CREB signaling in the prostate gland	
Principal Investigator: [name]., [name], D.V.M, Ph.D.	

Inclusion Criteria (as outlined in study protocol)	Criteria is met	Criteria is NOT met	Source Used to Confirm * (Please document dates and lab results)
Men > 18 years of age			
Patients undergoing prostate biopsy or prostatectomy			
Individuals able to understand and willing to sign an IRB-approved informed consent document			
Exclusion Criteria (as outlined in study protocol)	Criteria NOT present	Criteria is present	Source Used to Confirm * (Please document dates and lab results)
Men taking propranolol daily for any reason are excluded			
Men with baseline SBP <120 or HR <63			
Men unable to swallow pills			
History of current or past medical or psychiatric illness that would make participation difficult or not feasible at the discretion of the principal investigator or co-investigators			

This subject is  eligible /  ineligible for participation in this study.

WISER Assigned PID: \_\_\_\_\_

Signature of research professional confirming eligibility: \_\_\_\_\_

Date: \_\_\_\_\_

Signature of Treating Physician\*\*: \_\_\_\_\_

Date: \_\_\_\_\_

\* Examples of source documents include clinic note, pathology report, laboratory results, etc. When listing the source, specifically state which document in the medical record was used to assess eligibility. Also include the date on the document. Example: "Pathology report, 01/01/14" or "Clinic note, 01/01/14"

\*\*Principal Investigator signature can be obtained following registration if needed

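### AV block is not a named exclusion, although the protocol lists its worsening as a propranolol effect; keeping such a man out depends on how a discretionary clause about participation is read

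*Combined protocol and SAP*

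**What the plan says.** Section 3.2 has four exclusions, and Appendix A repeats them without adding any.

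- Line 1: "Men taking propranolol daily for any reason are excluded".
- Line 2: "Men with baseline SBP <120 or HR <63".
- Line 3: inability to swallow pills.
- Line 4, the only one on medical history, covers any current or past medical or psychiatric "illness that would make participation difficult or not feasible at the discretion of the principal investigator or co-investigators".

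Section 4.1 makes the checklist the first step of registration and tells staff: "Fax/e-mail ALL eligibility source documents with registration". Appendix A has a source column for each criterion and signature lines for the research professional and the treating physician.

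Section 13.1 gives the known effects of the drug. The cardiovascular entry begins "Bradycardia; congestive heart failure; intensification of AV block; hypotension". Elsewhere the list has "Respiratory: Bronchospasm" and anaphylactic reactions.

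Section 4.2 adds a hold on the day of dosing if SBP is below 120 or HR below 63, for biopsy and prostatectomy alike. For prostatectomy there is also a check by the anesthesiologist for low pressure and slow heart rate. A standard-of-care history and physical precedes the procedure, and Appendix G records all medications.

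**The concern.** The protocol recognizes that propranolol can make existing AV block worse, but it writes no rule for the man who has it. Staff can follow every specific criterion and still give him the drug. Two investigators could also reach different decisions about the same man, because the one clause that might exclude him names no condition and does not mention the drug.

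The issue is patient safety. None of the objectives in sections 2.1 and 2.2 concerns benefit to the participant; the dose is given so that tissue and plasma markers can be measured. Section 8.4 undertakes to review the exclusion criteria if the dose goes up to 80 mg, which shows that the authors see exclusions as a drug-safety tool. There is no similar step for the 40 mg starting dose.

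**Working it through.** The plan has no figure on this point to reproduce. The check is to take one man through every safeguard in order. Suppose he has AV block, SBP 135 and HR 75, takes no propranolol, and can swallow pills.

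1. **Exclusion 1.** He takes no propranolol, so he passes.
2. **Exclusion 2.** 135 is not below 120 and 75 is not below 63, so he passes. A man whose block slows his heart rate below 63 would be caught here, but by his rate and not by his history.
3. **Exclusion 3.** He can swallow pills, so he passes.
4. **Exclusion 4.** The outcome is undetermined. Taking one tablet before a procedure already scheduled is feasible for him, so a literal reader could mark the criterion as not present. A reader who counts drug risk as a difficulty of participation would exclude him.
5. **Sign-off in Appendix A.** A treating physician's signature is asked for. The footnote marked on that line lets the principal investigator's signature follow registration, and under section 4.1 the registrar gives the randomized assignment as part of registration. Physician review before assignment is therefore likely but not guaranteed by the form.
6. **History, physical and medication list (section 4.2, Appendix G).** These may bring the block to light. No exclusion or hold rule refers to what they find, and Appendix G has no cardiac history item.
7. **Dosing-day hold (section 4.2).** It uses the same limits as exclusion 2, so it is not triggered.
8. **Anesthesiologist's check (section 4.2).** It is described for prostatectomy only, and for low pressure and slow rate only. His history does not trigger it.
9. **After the dose (sections 6.1 and 8.4).** Grade 3 or worse bradycardia or hypotension, or a propranolol-related event that prolongs the post-anesthesia stay, counts as a safety concern and locks the study for 24 hours. Blood pressure is checked at 3 and 4 hours. All adverse events are reviewed after 10 patients, 5 per group. These steps come after he has taken the drug.

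Counts from the text:

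| Item | Count |
|---|---|
| Exclusion lines in 3.2 | 4 |
| Lines with a measurable limit | 1 (line 2) |
| Lines naming AV block | 0 |
| Men assigned propranolol (section 3.0) | 30 of 60, more if recruitment is extended |

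Only step 4 is an eligibility rule capable of excluding him, and its wording leaves the result open.

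**The case against.** The strongest reply is that exclusion 4 already does this job. It covers any medical illness, past or present. It is marked and sourced for every man before registration. Participation includes possible assignment to propranolol, so an illness that makes the drug unsafe can reasonably be read as making participation difficult. Nothing in the text forbids that reading. An investigator discusses the study with patients, a physician's signature is on the form, and a full history is taken. Exposure is a single 40 mg tablet, and safety is handled patient by patient as well as at the 10-patient review.

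Much of this stands. The clause is a real gate, and a careful investigator would probably use it. It would be wrong to infer that such men go unscreened or that the plan intends to dose them. What remains is that none of these safeguards is an explicit drug-safety rule on AV block, and the post-dose triggers cannot replace screening.

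A reader might also infer that the protocol shows airway disease, heart failure and beta-blocker allergy to be equally clear omissions. The documents do not support that. Section 13.1 is a list of adverse effects, not contraindications, and includes many other entries. It gives bronchospasm, heart failure and anaphylaxis as harms without saying that a history raises the risk. Only the AV block entry, through the word intensification, refers to disease already present. The other three need a clinical judgement that the documents do not supply.

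**Conclusion.** The point holds for AV block. As written, a man with AV block and acceptable vital signs meets every specific criterion, and whether he is dosed depends on the reading of a discretionary clause framed around participation. For airway disease, heart failure and hypersensitivity, the conclusion is only that the study physicians should settle the matter in advance.

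This should be changed, but as an inexpensive improvement to an existing gate; the gate is not absent. The conclusion rests on the wording of sections 3.2, 4.2 and 13.1 and of Appendix A, and on no assumed prevalence. The documents say neither how common AV block is among these men nor how often one dose would harm them, so no frequency of harm can be given. A reader might want to assume a prevalence and calculate the chance of at least one affected man among the 30. That would be the chance of a history being present if exclusion 4 caught nobody, not the chance of harm, and it would not strengthen the point.

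**What to change.** 1. Add AV block as a named, checkable exclusion in section 3.2 and Appendix A.
2. Extend exclusion 4 so that, besides difficulty and infeasibility, it covers illness that would make the study drug unsafe for the patient.
3. Have the study physicians decide before enrollment, and record as a clinical judgement, whether the same line should also name bronchospastic airway disease, heart failure and hypersensitivity to beta-blockers, and at what threshold.
4. Confirm the line from the existing history and physical before registration, in both arms. Finding the condition only on the dosing day would lead to drug being withheld in the propranolol group alone.

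The cost is one checklist line and a few words in exclusion 4, with no new test or visit. A few otherwise eligible men are lost. Because they would be screened out before registration, they take no places among the 60, and the target of 25 evaluable men per group is unchanged.

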### **3.3 Inclusion of Women and Minorities**

Men of all races and ethnicities who meet the above-described eligibility criteria are eligible to participate. Due to the sex specific nature of prostate cancer, women will not be included in this study.

Based on WFBCCC population estimates and based on the sample size of 60 patients total for this study, we plan to enroll approximately 15% Black

or African American (N=9). Given the low rates and/or population statistics in our catchment area we expect no or very low accruals within the Asian, American Indian, or Pacific Islander populations. Additionally, we may expect approximately 5% of the sample to be Hispanic, which may account for an N = 3 Hispanic individuals. Should we not meet or exceed these estimates, the PI will engage the Cancer Center Health Equity Advisory Group to discuss strategies to enhance recruitment in these target populations.

### **3.4 Accrual**

Five (5) individuals per month for one year

## **4.0 Methods**

### **4.1 Registration Procedures**

All patients entered on any WFBCCC trial, whether treatment, companion, or cancer control trial, **must** be registered, within 24 hours of Informed Consent, into WISER. Patients **must** be registered prior to the initiation of treatment.

You must perform the following steps in order to ensure prompt registration of your patient:

1. Complete the Eligibility Checklist (Appendix A)
2. Complete the Protocol Registration Form (Appendix B)
3. Alert the Cancer Center registrar by phone, *and then* send the signed Informed Consent Form, Eligibility Checklist and Protocol Registration Form to the registrar, either by fax or e-mail.

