#### **4.2 Methods**

#### **Compare activation of ADRB2/PKA/BAD signaling pathway in the prostate glands of men who take or do not take ADRB2-selective beta blockers**

##### **Patients scheduled for prostate biopsy.**

The research staff screens the OR and clinic schedules for potential patients and provides a list to the investigator. [name] or co-Investigator will discuss the study with the patient and inform the research nurse or coordinator (research staff) about the patients who agreed to participate in the study. Research staff will inform Tissue Procurement Lab (Director [name]; [name], Tumor Procurement Coordinator) and courier about the scheduled date and time when prostate samples will be collected.

On the day of sample collection [name] lab will prepare box with dry ice for prostate biopsy samples, a box with wet ice for blood samples as well as 2 ml cryovials (Corning, cat#430488) to collect biopsies and tubes to collect blood (Na heparin, green-capped tube, 10 ml total blood volume).

Courier will pick up boxes from Tissue Procurement Lab (Director [name]; [name], [contact]) and deliver to research staff at Charlois clinic ([name]).

Recruited patients scheduled for prostate biopsy will be randomized into two groups. Group one will receive 40 mg propranolol given by research nurse 2 hours prior to prostate biopsy. The research nurse should withhold drug and contact treating physician if SBP <120 or HR < 63. Group two will receive no treatment.

All patients will fill out stress surveys on the biopsy day.

All patients will give approximately 10 mL of blood approximately 20 min prior to prostate biopsy to test plasma catecholamine levels (collected in 10 mL green top tube (sodium heparin) and sent on ice within 1 hour to clinical lab for processing) and propranolol level (collected in 10 mL green top tube (sodium heparin) and sent on ice to The Tissue Procurement lab for processing and storage as described below). For group one that takes propranolol, this blood sample will be drawn at 1.5 -2 hours after taking the propranolol tablet.

For the biopsy, at least 1 core of the prostate specimen is to be flash frozen (on dry ice -80C) for laboratory analysis. Each biopsy sample will be collected into separate cryovials. The samples will be picked up by courier at Charlois clinic and delivered to Tissue Procurement laboratory.. The tissue samples will be frozen at -80 C.

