### 7.2 Secondary Outcomes

- 7.2.1 BAD phosphorylation by western blot in prostate tissue from men two hours after taking or not taking propranolol prior to prostate biopsy
- 7.2.2 Difference in levels of transcripts that reflect ADRB2/PKA activation as measured by real-time PCR in prostate tissue from men two hours after taking or not taking propranolol prior to prostate biopsy or prostatectomy.
- 7.2.3 Plasma propranolol levels as measured by fluorometric detection from men two hours after taking or not taking propranolol prior to prostate biopsy or prostatectomy.
- 7.2.4 Plasma catecholamine levels (including epinephrine) measured by ELISA from men two hours after taking or not taking propranolol prior to prostate biopsy or prostatectomy.
- 7.2.5 Self-perceived stress as measured by The Perceived Stress Questionnaire (Appendix C) from men on the day of surgery before taking propranolol, prior to prostate biopsy or prostatectomy.
- 7.2.6 Distress score as measured by The Distress Thermometer (Appendix D) from men on the day of surgery before taking propranolol, prior to prostate biopsy or prostatectomy.

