### Randomization

This patient has been randomly assigned to the following treatment arm (Check one):

\_\_\_\_\_ Propranolol and Prostate biopsy or prostatectomy (Group 1)

\_\_\_\_\_ Prostate biopsy or prostatectomy only (Group 2)

Randomization Recorded by: \_\_\_\_\_ Date \_\_\_\_\_ / \_\_\_\_\_ / \_\_\_\_\_ Time \_\_\_\_\_

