#### Post-randomization Activities (1-2hr Post-Drug if randomized to Group 1)

Blood Draw:  Yes  No Time \_\_\_\_\_ Initials \_\_\_\_\_

Perceived Stress Survey:  Yes  No Time: \_\_\_\_\_ Initials \_\_\_\_\_  
Score \_\_\_\_\_

Distress Thermometer Survey:  Yes  No Time \_\_\_\_\_ Initials \_\_\_\_\_  
Score \_\_\_\_\_

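### The Surgery Day Worksheet puts the stress and distress surveys after group assignment and, in Group 1, after the drug, which contradicts the outcome definitions in 7.2.5 and 7.2.6

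*Combined protocol and SAP*

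**What the plan says.** **Assignment.** Section 4.1 says a patient must "be registered, within 24 hours of Informed Consent, into WISER" and must "be registered prior to the initiation of treatment". Among the steps by which the registrar completes registration is "Randomized Group Assignment". The registration form in Appendix B then records it: "This patient has been randomly assigned to the following treatment arm".

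**Control.** Section 4.2 says "Group two will receive no treatment". No placebo is described, nor any step that hides the arm until the surveys are done.

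**Surveys.** Section 4.2 says of biopsy patients: "All patients will fill out stress surveys on the biopsy day". For prostatectomy patients it asks only that the surveys precede the operation. Outcomes 7.2.5 (perceived stress) and 7.2.6 (distress) take the scores "from men on the day of surgery before taking propranolol". Appendix N runs in a different order: group assignment and drug administration first, then a block headed "Post-randomization Activities (1-2hr Post-Drug if randomized to Group 1" that holds the blood draw and both surveys.

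**Use of the scores.** Section 8.3 compares stress and distress between the randomised groups with two-sample t-tests. Objectives 2.2.5 and 2.2.6 relate the scores to blood catecholamines and to pathway activation in tissue.

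**The concern.** The trial's hypothesis is that stress drives the pathway under study, so the stress and distress scores are meant to describe the man before treatment. Measured before assignment, they can differ between arms only by chance. Measured after assignment, with the arm visible, they can also differ because a man knows whether he will get a tablet. Measured after dosing, Group 1 scores can reflect the drug itself. Section 1.0 cites a randomised study in which propranolol reduced anxiety in surgical patients, so this protocol cannot treat that as remote.

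Two uses of the scores are at stake. A difference found by the section 8.3 t-tests could not be attributed to chance, to the drug or to knowledge of the arm. For objectives 2.2.5 and 2.2.6, a score altered by the drug in one arm would be related to catecholamine and tissue measurements made in the same treated men, so part of any association could come from treatment.

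**Working it through.** **1. Order of events in each source.**

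| Source | Surveys relative to assignment | Surveys relative to drug (Group 1) |
|---|---|---|
| Section 4.1, with section 4.2 | After: assignment completes registration, which must precede treatment and follow consent within 24 hours; surveys are on the procedure day | Not fixed by rule |
| Outcomes 7.2.5 and 7.2.6 | Not stated | Before |
| Appendix N | After | 1 to 2 hours after |

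The last two rows cannot both be followed in Group 1. No source requires the surveys to come before assignment or before the patient learns his arm.

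**2. The plan's own figure.** Section 8.1 gives 80% power for a difference of 0.21 with SD 0.26, 25 per group, two-sided alpha 0.05. The noncentrality is 0.21 / (0.26 × √(2/25)) = 2.856 on 48 degrees of freedom, with critical value 2.011. Power is 79.9%, so the figure reproduces. It concerns CREB phosphorylation and is not in dispute. It confirms the method used next.

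**3. Sensitivity of the survey t-tests.**

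Inputs:
- n = 30 per arm (section 3.0). A survey score does not need evaluable tissue, so the enrolled number applies.
- Two-sided alpha 0.05. Section 8.3 states none, so this is carried over from section 8.1 as an assumption.
- No true difference in stress between arms.
- A shift of d SD in one arm, from the drug or from knowing the arm. This is assumed, since the documents give no value, and is therefore shown as a range.

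The noncentrality is d × √(30/2) = 3.873 × d, on 58 degrees of freedom, with critical value 2.002.

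| Assumed shift d | Noncentrality | Rejection rate |
|---|---|---|
| 0 | 0 | 5.0% |
| 0.1 SD | 0.387 | 6.7% |
| 0.2 SD | 0.775 | 11.9% |
| 0.3 SD | 1.162 | 20.8% |
| 0.4 SD | 1.549 | 33.2% |

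These rates apply to the between-arm t-test. They do not measure bias in the associations under 2.2.5 and 2.2.6, which would need correlations that the documents do not give.

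**The case against.** **The shift may be small.** The stress form asks about the last two weeks, and the Distress Thermometer about the past week including today. Knowing that one will or will not take a single tablet may hardly move such answers. This stands, and it is why the range starts at 0.1 SD, where the excess over 5% is slight. It is weaker for the thermometer, which includes the procedure day.

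**The narrative favours surveys first.** The experimental plans in section 4.2 mention the surveys before the drug, and Appendix N has a time field for the dose and for each survey, so the actual order could be checked afterwards. That stands too. But the worksheet is the form staff work from on the day, and its heading tells them the opposite.

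**Knowledge of the arm is inferred.** The documents do not say when a patient is told his arm or how long passes between consent and procedure. Assignment before the surveys is documented. Disclosure before them is possible but not established, except that a man who has already taken the tablet knows.

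**Stronger readings.** Three inferences are tempting, and the documents do not support them.
- *That men withdrawing after assignment would raise the false-positive rate of the primary comparison.* A figure for this needs the withdrawals to be selected on CREB phosphorylation, which is measured in tissue taken afterwards. Selection could act only through a correlate, and no correlation is given.
- *That the blood pressure and heart rate check at dosing removes men from Group 1.* The same limits (SBP below 120, HR below 63) are exclusion criteria in section 3.2, confirmed on the checklist before registration. At dosing, section 4.2 says the drug is withheld, not that the man leaves the study.
- *That every man who withdraws is replaced.* Section 3.0 recruits more only if evaluable tumours fall below 25 in a group.

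**Conclusion.** The point holds for the two survey outcomes. Appendix N contradicts 7.2.5 and 7.2.6 on whether the surveys precede propranolol, and nothing in the plan places them before assignment. The contradiction needs no assumed figure. Its effect does: under an assumed shift of 0.1 to 0.4 SD, 30 per arm and a two-sided 5% test, the between-arm comparison rejects in 6.7% to 33% of trials with no true difference in stress. The recall windows make the lower end a fair possibility.

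The point does not reach the primary outcome, a laboratory ratio measured in tissue, and it is not evidence that losses after randomisation will be unequal. The change is worth making because it protects two stated outcomes and two objectives at almost no cost.

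**What to change.** **Main change.**
- Reconcile Appendix N with 7.2.5 and 7.2.6 by moving the two survey lines above the group assignment and the drug administration block. Leave only the blood draw under the post-drug heading.
- State in section 4.2, for biopsy and prostatectomy patients alike, that both surveys are completed before the patient is told his arm.

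The cost is a form revision and one sentence of protocol text. The completion-time fields already on the worksheet will show whether the order was kept.

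**Optional, where feasible.** Keep registration within 24 hours of consent but release the arm on the procedure day, once the surveys and the SBP and HR readings have been recorded for every man. This puts the surveys and readings before assignment as well as before disclosure. The costs are real:
- a release mechanism that works outside the registrar's hours (8:30 AM to 4:00 PM, Monday to Friday);
- drug ready for men not yet assigned, which the clinic's stock bottle covers at the Urology clinic but which at the main facility must come through the pharmacy (section 5.0);
- attendance by control patients early enough for a dose 2 hours beforehand.

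If these are too much, the main change alone resolves the contradiction and keeps the drug and disclosure of the arm out of the scores.
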